1.1 Identification on the medical device

The medical device subject to this clinical investigation is the:

"Chimaera™ Hip Fracture System – Trochanteric Nailing system", di hereinafter (Chimaera).

Chimaera is a trochanteric nail system classified as a class IIb medical device, manufactured and marketed by Orthofix Srl on the markets of the European Union and some markets outside the European Union starting from 02 May 2016.

Note:

In the present clinical investigation, only patients treated with nails with a length of 180 mm, hereinafter referred to as "short nail", will be observed.

[figure not shown]
1.2 Intended use

The Chimaera *Trochanteric Nail System* was developed for insertion into the intramedullary canal of the femur for the purpose of aligning, stabilizing, and fixing various types of fractures or deformations of the proximal femur in an adult population.

Chimaera is indicated for the treatment of fractures located in the pectrochanteric, intertrochanteric and subtrochanteric region of the femur, stable or unstable, or in combination with diaphyseal fractures extending distal up to 10 cm from the intercondylar fossa.

Note:

in accordance with the patient selection criteria, pectrochanteric, intertrochanteric and subtrochanteric fractures of the femur, which are treatable with the short version of the nail, will be observed during this clinical investigation, while diaphysiar fractures that should be treated with the long version of the nail will be excluded from the present clinical investigation.

The Chimaera has been designed for professional use only. Surgeons responsible for supervising the use of the product must possess a thorough understanding of orthopedic fixation procedures and must be familiar with the devices, instruments, and surgical procedure, including application and removal.

For further details please refer to the package insert "Instructions for use" published on:
http://abs.orthofix.it/db/resources/PQ_HFN.pdf

1.3 Detailed description of the device

The *Chimaera* is a system consisting of:

- Canulated intramedullary nails in titanium alloy, of various lengths and diameters.

In the present clinical investigation, only patients treated with nails of 180 mm length, hereinafter referred to as "short nail", with a proximal diameter of 15.5 mm and a distal diameter of 10 or 11 mm (Figure 1), with anatomical curvature that allows insertion into both the right and left femur, will be observed. For this reason, diaphysial fractures that can be treated with the long version of the nail, in accordance with the patient selection criteria, are excluded from the present clinical investigation.

[figure not shown]

Figure 1: Technical characteristics of the short nail

Figure 2: Handle for inserting the nail

The proximal part of the nail has a threaded hole that allows the nail to be connected to the handle by means of a locking tie-rod. The handle required for nail insertion (Figure 2) consists of a radiolucent carbon fiber structure with steel connection elements and has locking holes for some components of the insertion instrumentation such as guide wire guides, trocars, reamers and screwdrivers.

The proximal part of the nail also has two holes designed to allow the insertion of one or two cephalic screws: depending on the desired cervical-diaphyseal angle (CCD), there are two distinct versions of the short nail with proximal holes at 125° or 130° (Figure 3).

[figure not shown]

Figure 3: angles of the main and additional cephalic screw.

The distal tip of the nail has a tuning fork designed to lower the pressure exerted by the nail on the cortical of the femur and thus decrease the likelihood of peri-implantation fractures occurring.

- A mandatory main cephalic screw required for proximal nail locking to the femur (Figure 4) and an optional supplemental cephalic screw (Figure 5) to counteract rotational instability of the bone abutments where necessary.

Lag screw - sliding - Sterile

Figure 4: Main Cephalic Screw

Supplementary lag screw - Sterile

Figure 5: Secondary Cephalic Screw (Optional)

Both cephalic screws are marketed in telescopic (sliding) or fixed-length versions. In the present clinical investigation, only patients treated with telescopic screws designed to allow the fracture to compact and thus lower the probability that the screw protrudes from the head of the femur (serious complication called *cut out*) will be observed.

Both cephalic screws are also self-locking on the housing hole positioned on the head of the nail: this feature lowers the probability that the screws protrude laterally.

- Threaded screws for distal locking of the nail (Figure 6), which can be done with 3 different options, i.e. static, dynamic or static and potentially dynamizable later (Figure 7).

[figure not shown]

Figure 6: Distal Threaded Screw

[figure not shown]

Figure 7: Different Options for Distal Locking

- Blanking plugs at different protrusion levels to be inserted into the nail head (Figure 8).

Figure 8: Blanking caps

- Instruments for inserting (Figure 9) and removing (Figure 10) the nail.

[figure not shown]

[figure not shown]
Figure 9: Insertion tools

Figure 10: Nail removal tools

For further details regarding the components of the *Chimaera system*, please refer to the surgical technique published on: <http://abs.orthofix.it/db/resources/HF-1501-OPT-I1.pdf>.

1.4 Surgical procedure related to the use of the medical device.

The nails of the *Chimaera system* are inserted with anterograde access: the insertion point varies with the anatomy of each patient and generally coincides with the apex of the greater trochanter (Figure 11) or is slightly shifted to a more medial position.

Figure 11: Nail insertion point.

The insertion of the nail (Figure 12) is performed with the patient placed in a supine position with the help of a series of instruments according to the following macro-phases:

- Opening the insertion point.
- Bore of the medullary canal.
- Nail insertion.
- Proximal locking with one or two cephalic screws.
- Distal locking.
- Inserting the cap.

Figure 12: Short nail inserted and secured using 2 proximal screws and 1 distal screw.

For more details about the components of the *Chimaera system*, please refer to the surgical technique published on: <http://abs.orthofix.it/db/resources/HF-1501-OPT-I1.pdf>.

1.5 Indications for the traceability of the medical device.

The use of the *Chimaera* is already part of the normal clinical practice of the centers involved, so this device is not to be considered an experimental product. For this reason, the supply and traceability of the *Chimaera* at the centers involved will follow the standard commercial process of supplying medical devices.

2 Literature Analysis (Background)

Proximal femur fracture, commonly known as hip fracture, is one of the most frequent and serious injuries that can occur in elderly individuals.

They are classified into three types depending on the location: a) intracapsular fractures of the femoral neck (about 45% of PFFs); b) extracapsular fractures in the intertrochanteric region (about 45%); c) subtrochanteric

fractures (located between the lesser trochanter and the femoral isthmus, about 10%).¹ The distinction between intracapsular and extracapsular is important, because it addresses the likelihood of vascular impairment. Intracapsular fractures can damage the head of the small femur with the risk of avascular necrosis and/or non-union, or the management of these fractures. Extracapsular fractures (intertrochanteric or subtrochanteric) carry a minimal risk of vascular impairment, and their treatment focuses on anatomical reduction and stabilization with implants (such as nails or plates) to allow for early mobilization and loading during fracture healing.²

Hip fracture continues to be the most common injury in the elderly population. The incidence appears particularly high over the age of 75, when both the prevalence of osteoporosis increases (more than 45% for women, more than 18% for men) and the risk of falls and, therefore, often even low-energy trauma is sufficient to cause the rupture of the proximal portion of the femur. By 2050, the proportion of the world's population over 60 years of age will almost double from 12% to 22%, and the annual incidence of proximal femur fractures worldwide will increase proportionately to 6.26 million.³

Hip fracture is now considered one of the major social and health emergencies in the geriatric field. Despite recent significant improvements in the field of surgery and rehabilitation, hip fracture remains a difficult challenge for patients, their families, and orthopedic surgeons. In fact, these fractures often have a strong impact on the patient's mobility and therefore on the performance of activities of daily living. All this translates into a dramatic deterioration in quality of life with a significantly reduced life expectancy.

In fact, about 10% of patients over 75 years of age who suffer a hip fracture die within 30 days of surgery at cause of intra- and post-operative complications that aggravate a general state of health already compromised by pre-existing comorbidities. In addition, the drastic change in life triggered by the severe disability caused by this fracture, which often leads to a substantial loss of autonomy, causes the 1-year mortality rate to rise between 14% and 36%.⁵ 42% of survivors do not return to pre-fracture mobility, 35% are unable to walk independently, 20% are unable to shop independently, and approximately 20% enter a long-term care facility during the first year after a fracture.⁴

In an attempt to lengthen the expectations and quality of life of these patients, the most recent guidelines suggest a multidisciplinary approach for the treatment of unstable hip fractures that involves, where possible, the close collaboration of different specialists such as the orthopedist, the geriatrician, the anesthesiologist, the cardiologist and the physiatrist. Although a consensus on the best possible treatment has not yet been found, several studies demonstrate a real benefit in the use of multidisciplinary protocols that always provide for timely surgical treatment of the fracture.^{5,6}

To date, there are several treatment options available for unstable hip fractures, each with advantages and disadvantages, including external fixation systems, internal fixation systems and partial or total hip replacement. In the field of internal fixation, the use of intramedullary nails has become increasingly popular due to the biomechanical advantages they provide in many indications compared to other synthetic media such as plates or dynamic cephalic screws.

However, the percentage of complications considered serious, i.e. requiring reoperation, associated with intramedullary nail treatment, such as cut-out, lateral protrusion of the cephalic screw and peri-implantation fractures, remains clinically significant (overall they can affect up to 30% of patients treated).

The *Chimaera* developed by Orthofix Srl is an intramedullary nail also indicated for the treatment of proximal femur fractures that integrates technical features specifically designed to decrease the probability of encountering the most serious and frequent complications in this type of treatment.

These technical characteristics are: a) the double telescopic cephalic screw, designed to counteract the rotational instability of the bone stumps and allow the compacting of the fracture, lowers the probability of cut out; b) the locking mechanism of the cephalic screws on the nail lowers the probability that the screws

protrude laterally; c) the tuning fork positioned on the distal tip of the nail, designed to lower the pressure exerted by the device on the cortical femur, decreases the likelihood of peri-implantation fractures.

3 Rationale for clinical investigation

Orthofix Srl has developed and placed on the European market the Chimaera after carrying out an evaluation of the clinical performance and safety of the medical device on the basis of biomechanical tests and clinical data obtained from scientific publications on equivalent products (on request, more details available in Technical File A.1.10 archived at the Sponsor).

The outcome of this pre-market assessment established that the Chimaera meets the necessary requirements for CE marking, in particular it has an acceptable risk/benefit ratio when used according to the manufacturer's indications for use.

To date, more than 3000 treatments have been carried out in Europe with Chimaera: the frequencies of serious complications received by Orthofix Srl through the passive medical device vigilance system are lower than those reported in the literature for equivalent nails on the market for several years. This first evidence seems to confirm the efficacy and safety of the technical characteristics integrated into the device; however it must be integrated with clinical data collected and analyzed with the methodology of a clinical investigation.

The data obtained from this Clinical Investigation will be used to complement the pre-market clinical evaluation carried out on the Chimaera with post-market clinical data from the use of the device in a representative number of patients and users observed in normal clinical practice.

4 Ethical considerations

The contents of this Protocol comply with the recognized ethical principles for clinical trials, the principles of good clinical practice (ICH-GCP Guidelines) on clinical investigations with medical devices and the applicable regulations (UNI EN ISO 14155).

The procedures described in this Protocol are part of the normal clinical practice of the Centers involved. In fact, this clinical investigation is observational so it will not change the clinical protocols currently in use in the Centers involved, nor does it involve additional risks for patients and investigators.

Participation in research is free, not bound by interests and motivated by a spontaneous collaborative contribution to acquire data of common interest. There is no direct compensation for physicians participating in this Clinical Investigation.

The Investigator in charge of each Site shall ensure that this Clinical Investigation is conducted in accordance with the Declaration of Helsinki and with national and international laws and regulations that ensure the greatest possible protection for the patient.

The procedures described in this Protocol will be applied only after the evaluation and possible approval of the contents by the relevant Ethics Committees of each participating Center.

The physician's decision to treat a patient with Chimaera is entirely independent of the patient's willingness to participate or not participate in the Clinical Investigation, i.e., the physician will make such a decision solely based on his or her own medical considerations in the best interests of the patient before seeking consent to participate in the Clinical Investigation. Only after the physician has decided to treat a patient with Chimaera will he ask the eligible patient for consent to participate in the Clinical Investigation and verify the inclusion and exclusion criteria. It is understood that such a patient will receive the same type of treatment and all related care even if he or she decides not to participate in the Clinical Investigation or is not eligible to participate.

Before enrolling the first patient, each Investigator will also be adequately instructed by Orthofix Srl on the contents of this protocol, the use of the electronic system that will be used for data collection and the procedures of the clinical investigation.

4.1 Identification of subjects and confidentiality

The Investigator will assign a unique, predefined and sequential code to each enrolled patient. Only the Investigator will be able to associate this code with the patient's name for communications relating to the Clinical Investigation or for the compilation of the data collection form, therefore the pseudo-anonymization of the patient will be guaranteed.

As stated in the informed consent form, the confidentiality of patient data will be always maintained. Each patient (or his/her legal representative) will be informed by the Investigator that his/her clinical documentation may be audited by the Sponsor's representatives (monitor) or by regulatory authorities.

Each patient, at the same time as signing the consent for participation in the Clinical Investigation, will also be asked to sign for the collection and processing of clinical data that will be collected without direct identifiers and will be reprocessed anonymously. In addition, security measures will be applied appropriate to the type of data and the type of processing, in accordance with the requirements of GDPR 679/2016 and in compliance with the Guidelines for the processing of personal data in the context of clinical trials of medicinal products – 24 July 2008 (Official Gazette no. 190 of 14 August 2008).

Finally, patients will be able to exercise the rights referred to in European Regulation no. 679/2016 art. 7 of the Privacy Code (e.g. access your personal data, integrate them, update them, rectify them, limit them, oppose processing for legitimate reasons, request their portability, etc.) by contacting the Site directly or, through it, the Promoter. Furthermore, no further data concerning the patient will be collected, without prejudice to the use of any data already collected to determine, without altering them, the results of the clinical investigation.

4.2 How to obtain informed consent

Note:

An adult patient with previously untreated proximal femur fracture who, based on the free judgment of the Investigator, will have a regular indication for surgical treatment with Chimaera will be considered eligible for participation in the clinical investigation.

4.2.1 Patients able to give consent personally

Before taking part in the Clinical Investigation, any eligible patient capable of expressing valid consent personally, understood to be of sound mind and willing and able to affix his/her signature and date on the form:

1. You will be informed of the possibility, voluntary, of participating in the clinical investigation and that, if you agree to participate, you may refuse to continue the investigation at any time without prejudice to subsequent treatment;
2. will be informed about the potential benefits for the scientific community and for other patients deriving from the increase in the scientific knowledge generated by the survey;
3. if interested, through a specific information notice you will receive adequate information on the purpose of the clinical investigation, its characteristics (observational and non-interventional), the schedule of visits, the expected duration of the same, your responsibilities and the methods of collecting and processing clinical data;
4. he/she will be given the necessary time to receive from the Investigator all clarifications and additional information he/she deems necessary;
5. if he decides to participate in the clinical investigation, before carrying out the first visit provided for by the Protocol, he will sign and give the informed consent of which he will keep a copy.

It is understood that:

- as specified in the form for obtaining consent, by signing, the patient expresses his/her consent both for participation in the survey and for the collection and processing of clinical data;
- if deemed necessary in the best interest of the patient's health, the Investigator may decide to discontinue participation in the investigation without the consent of the patient who will be informed of the decision and the related reasons.

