4.3 Obtaining informed consent in emergency conditions

Whenever objectively possible, the consent form will always be signed and dated by the patient or respondent (witness, legal guardian or family member/cohabitant of the patient) prior to verification of inclusion criteria, which is the first procedure under this Protocol.

In emergency situations, i.e. when due to:

- the patient's medical condition and/or;
- the clinical context in which the Investigator and/or will operate;
- of the impossibility of the respondent to be immediately present.

It will not be possible to provide information on the survey and receive any clarifications; the patient or the respondent will be informed as soon as possible about the possibility of participating in this observational survey and will be able to express their consent even later according to the methods described above.

5 Information for the general practitioner

The Sponsor with the documentation relating to this Clinical Investigation will provide the Investigators with a pre-printed information letter to the treating physician containing all relevant information regarding this observational investigation. Once the patient inclusion and exclusion criteria have been verified, if the patient will indeed be included in the investigation, the Investigator will fill in the pre-printed letter with the patient's data and deliver this letter to the patient himself or to the respondent subject who will be in charge of delivering it for information to the general practitioner.

6 Any news regarding the medical device under investigation

In the event that, during the course of this Clinical Investigation, the Investigator or the Sponsor becomes aware of news regarding the Chimaera system, deriving from this investigation or from market reports (*complaints*), which may influence the decision of the patient (or the respondent) to participate in the Clinical Investigation, it will be the Investigator's responsibility to promptly inform each subject already enrolled in the Investigation.

It is understood that, following this new information made available, the patient (or respondent) or the Investigator may refuse to continue the investigation at any time they wish without prejudice to subsequent care.

7 Vulnerable population and treatment in emergency circumstances

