Clinical data from the study will be recorded in the patient's medical chart and entered a validated electronic data capture system provided by Orthofix Srl.

Patients who, for any reason, decide to withdraw their consent to participate in the study before completing the final follow-up visit will continue to receive the same standard of care they would have received had they completed the study.

Note:

The visits and procedures described above are summarized in the patient treatment schedule and in the table of procedures applicable to each visit below.

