9.15 Interruption and withdrawal of subjects from clinical investigation

A patient will be discontinued prematurely from the study if they do not complete the last protocol-scheduled follow-up visit due to any of the following causes:

- the patient withdraws consent to participate in the study;
- one of the inclusion criteria will be dropped or an exclusion criterion will occur;
- lack of response to treatment that generates an unacceptable risk for the patient and prevents the continuation of the treatment covered by this observational scientific research;
- onset of a serious adverse event that generates an unacceptable risk for the patient and prevents the continuation of treatment;
- the patient does not follow the procedures of the clinical protocol provided by his doctor;
- decision of the Investigator in the interest of the patient;
- patient no longer available (lost to follow-up);
- death of the patient during the study period.

Patients who are prematurely discontinued will be reported in the data collection form through the appropriate discontinuation visit. The Investigator will have the obligation to report to the Sponsor the patients who are prematurely discontinued and, if the patient is not assessable, or is discontinued before the end of the treatment period for supposed recovery scheduled for the control visit at the third month after the operation), may agree with the Sponsor on the replacement of the patient according to the following procedure.

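### An Investigator may end participation on health grounds, and nothing requires second-operation status to be obtained to Month 6 afterwards, so later events can be missed from the primary percentage

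*Combined protocol and SAP*

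**What the plan says.** **The exit rule.** Section 4.2.1 allows that "if deemed necessary in the best interest of the patient's health, the Investigator may decide to discontinue participation in the investigation without the consent" (the patient's); the decision and the reasons are then explained to the patient. The list of causes in Section 9.15 includes "decision of the Investigator in the interest of the patient". It also includes lack of response to treatment and "onset of a serious adverse event that generates an unacceptable risk for the patient and prevents the continuation of treatment".

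**Effect of participation on care.** Section 4 states that "this clinical investigation is observational so it will not change the clinical protocols currently in use in the Centers involved", and that "such a patient will receive the same type of treatment and all related care even if he or she decides not to participate". Section 9.11 says that patients who withdraw consent "will continue to receive the same standard of care they would have received had they completed the study".

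**Endpoint and evaluability.** The primary endpoint (Section 9.4) is the percentage of patients who need a second operation within 6 months because of serious device-related events. Section 9.14 calls a patient evaluable once the Month 3 visit (Visit 4) is completed. A patient discontinued before then is not evaluable and may be replaced during the recruitment period (Sections 9.15 and 9.16).

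**Data on discontinued patients.** They have a discontinuation visit and are reported to the Sponsor (Section 9.15). Their data, including those of replaced patients, are collected, stored and analysed (Section 9.16). Section 18 presents the primary endpoint as a percentage with a 95% confidence interval. It does not define the denominator or say how discontinued patients enter it.

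**The concern.** The decision to end participation under this rule rests on how the patient is doing. A patient doing badly with the implant may be both more likely to leave and more likely to be reoperated later. If nobody looks for the reoperation after the exit, it never reaches the numerator. The error then runs mainly one way, towards a lower percentage and a more reassuring upper limit.

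Two features of the plan add to this. Evaluability is settled at Month 3, while the endpoint runs to Month 6, so a patient who leaves in between can count as evaluable with the outcome unknown. A patient who leaves before Month 3 can be replaced by one whose course is not linked to that exit. Section 18 says the data will be used to confirm that the device is safe and effective, so an understated percentage would matter even though no hypothesis is tested.

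**Working it through.** **Inputs**
- Expected primary percentage: no more than 6% (Section 18).
- 400 enrolled to give 300 evaluable, with about 25% premature withdrawal (Sections 9.7 and 18).
- Sizing target: upper 95% limit below 10%, exact binomial (Section 18).
- Number of reoperations missed after an Investigator-led exit: not given. Values below are assumptions.

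**Reproducing the plan.** The upper limit is the 0.975 quantile of the beta distribution with parameters x + 1 and n − x.

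| Percentage | x / n | Computed | Stated |
|---|---|---|---|
| 3% | 3/100 | 8.518% | 8.518% |
| 4% | 4/100 | 9.926% | 9.926% |
| 5% | 8/160 | 9.614% | 9.614% |
| 6% | 15/250 | 9.703% | 9.703% |
| 7% | 28/400 | 9.958% | 9.958% |

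Enrolment: 300 / (1 − 0.25) = 400. The plan's figures are correct and are not in dispute.

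**Direction of the error.** Let x be the true events among n patients, m the patients who exit, and k those of the m who are reoperated after the exit and before Month 6.
- If the m patients drop out of the analysis, which is one reading for exits before Month 3, the result is (x − k)/(n − m). This is below x/n whenever k/m exceeds x/n, that is, whenever those who leave are reoperated more often than average. If they are reoperated at the average rate, there is no bias, only lost precision.
- If they stay in the denominator as event-free, which is one reading for exits between Month 3 and Month 6, the result is (x − k)/n. It is low by k/n. With n = 300, each missed event costs 1/300 = 0.33 percentage points.

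**Illustration, n = 300.** Here m = k, so every patient lost is one who is later reoperated. That is the extreme case for a given m.

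| True events | Missed (k) | Dropped from the analysis | Upper limit | Kept as event-free | Upper limit |
|---|---|---|---|---|---|
| 18 (6.0%) | 0 | 18/300 = 6.00% | 9.32% | 18/300 = 6.00% | 9.32% |
| 18 | 3 | 15/297 = 5.05% | 8.19% | 15/300 = 5.00% | 8.11% |
| 18 | 6 | 12/294 = 4.08% | 7.02% | 12/300 = 4.00% | 6.88% |
| 18 | 9 | 9/291 = 3.09% | 5.79% | 9/300 = 3.00% | 5.62% |
| 21 (7.0%) | 0 | 21/300 = 7.00% | 10.50% | 21/300 = 7.00% | 10.50% |
| 21 | 2 | 19/298 = 6.38% | 9.78% | 19/300 = 6.33% | 9.71% |

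At the plan's own 6%, the upper limit is below 10% with or without losses, so only the estimate and the interval shift. At 7%, two missed events move the upper limit from above the target to below it.

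**The case against.** **Events are kept, not removed.** A reader might infer that the rule takes reoperations out of the count, or that data collection stops once the Investigator acts. The documents do not say so. The rule is permissive, and Section 9.16 commits the Sponsor to analysing data from discontinued and replaced patients. Section 10 plans full monitoring of endpoint variables and adverse events. The sentence in Section 4.1 about collecting no further data sits in the paragraph on patients' privacy rights. This stands: only events after the exit are at risk, and the defect is silence, not an instruction. But a commitment to analyse data is not a duty to look for new events.

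**The clause may have a purpose.** A reader might infer from Section 4 ("it will not change the clinical protocols currently in use in the Centers involved, nor does it involve additional risks for patients") that ending participation can never serve the patient's health. That goes too far. Sections 9.5 and 9.14 recognise that these patients are hard to move, so sparing a frail patient a visit is a plausible reason. The Section 9.11 assurance concerns patients who withdraw consent. The clause need not be deleted.

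**Section 6 is a different matter.** It says that "the patient (or respondent) or the Investigator may refuse to continue the investigation at any time they wish", but only after news about the device. It does not concern selecting patients by their state of health and is not evidence for this mechanism.

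**Other causes in Section 9.15 are more direct.** The serious-adverse-event and lack-of-response items are closer to the endpoint, and the Month 3 definition of evaluable adds to the problem. This is fair, and the remedy should cover those causes too. It does not close the present route, which needs only the Investigator's judgement.

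**Reach and size.** The Section 9.15 list runs to the Month 12 visit, and an exit after Month 6 cannot affect the primary endpoint. The number of patients concerned may be small. Section 18 sets no safety threshold, so crossing 10% is a missed sizing aim and not a failed test. All of this stands.

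**Conclusion.** The point holds as a gap in follow-up. The plan permits an exit plausibly related to the outcome and does not require the 6-month endpoint status to be obtained after it. It also leaves open how such patients enter the numerator and denominator. Followed as written, it can miss later reoperations and understate the primary percentage.

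The size is unknown. The two-patient example, with an upper limit of 10.50% falling to 9.78%, assumes a true 7.0%, above the 6% the plan expects. It also assumes that both patients lost are reoperated after the exit and within Month 6. It shows how few missed events can matter and is not a forecast. If exits were unrelated to later reoperation and the patients were dropped from the analysis, there would be no bias.

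The documents do not support the stronger conclusions that the rule strips deteriorating patients' events from the data or that the clause is without any purpose. This is a cheap improvement worth making, not a fault that invalidates the study.

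**What to change.** Keep the Investigator's discretion to stop study visits or questionnaires, and add to Sections 4.2.1 and 9.15:

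- Discontinuation for any reason other than withdrawal of consent does not end collection of second-operation status. That status is taken to Month 6 from routine hospital records.
- The same sentence applies to the serious-adverse-event and lack-of-response causes in Section 9.15.

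In Sections 9.16 and 18, state that:

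- all implanted patients stay in the primary denominator;
- a replacement is an additional patient and does not take the replaced patient out of the analysis;
- discontinuations are tabulated by reason.

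The cost is wording in the protocol and the consent sheet, and a short chart check for the patients concerned. No extra visits are needed, and the planned enrolment of 400 does not change.
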